Rationale	
Open questions are still needed to be answered:
 
 - In the exclusive radiotherapy scenario, does ENI produce an overall or biochemical relapse free survival advantage over prostate only radiotherapy for intermediate/high/very high-risk cases? - If ADT is added to prostate only radiotherapy, in intermediate/high/very high-risk cases, ENI is any longer needed?

	
 - Is ENI, associated or not to ADT, linked with an OS or bRFS survival advantage in patients submitted to adjuvant postsurgical prostate radiotherapy? - Additional toxicity due to the larger volumes treated might be reduced by more sophisticated radiotherapy techniques when ENI is added to prostate? - How many Radiation Oncology centers use ENI to treat patients with intermediate/high/very high-risk prostate cancer, with or without ADT? - The data obtained from the present observational study will be helpful for designing a subsequent randomized controlled trial.
End-points	
Primary:
 
 - Overall survival; 
Secondary:
 
 - Cause-specific (CSS) and Biochemical Relapse Free survival (bRFS); - acute and late toxicity evaluation (rectal, bladder, bowel toxicity, according to CTCAE v.4 scale); - Quality of Life deterioration (according to the UCLA-PCI scale).
Study design	
This is a prospective, multicenter, observational cohort study aimed to describe the advantage/disadvantage of different treatments of patients with intermediate/high/very high risk prostate cancer, through a web-based database.
 
The study will include all consecutive patients affected by intermediate, high or very high-risk prostate cancer that fit to the inclusion criteria and who are evaluated at each Centre involved in the study. Patients may have already undergone or not to radical prostatectomy and/or pelvic lymphadenectomy.
 
Phase 1: Establishment of the network of Centers involved in the study Phase 2: Activation and recruitment of eligible cases Phase 3: Follow-up (1,3,6,12/18,24/30/36 months)

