In the adjuvant setting, sterilizing microscopic disease potentially persistent after radical surgery, particularly in high-risk patients, represents the rationale of adding WPRT to prostatic bed radiotherapy in pN0 patients. Goldner et al. evaluated the clinical impact of prostate only adjuvant RT in pN0 patients showing a 5-year biochemical relapse free survival of 100% and 58% in patients with a risk of nodal involvement <15% and >15%, respectively. These findings may be explained by a microscopic involvement of pelvic structures (lymph nodes, bone) other than prostate bed. However, the role of adjuvant post-surgical WPRT need to be validated by large prospective studies, not actually ongoing to our knowledge. [37, 38, 39, 40]. Moreover, no clear-cut guidelines are available about the usefulness of adding ADT to adjuvant RT in the different subsets of pN0 patients.

On the other hand, nodal involvement (pN1) is a strong negative prognostic factor and adjuvant RT in these patients may be useful to optimize loco-regional control deferring first or second line systemic therapies [41]. Actually, the standard adjuvant treatment for pN1 PCa patients is represented by long term ADT, but the association with WPRT might significantly increase survival outcomes [42]. A recent analysis conducted by SEER on “pN1 M0” PCa patients treated with adjuvant WPRT seems to confirm the benefit obtained by the association of WPRT with ADT, demonstrating a survival advantage for intermediate risk patients [43].

Conclusions, rationale and summary of the study

In conclusion, open questions about ENI for prostate cancer still remain:

1. In the exclusive radiotherapy scenario, does ENI produce an overall or biochemical relapse free survival advantage over prostate only radiotherapy for intermediate/high/very high risk cases?
2. If ADT is added to prostate only radiotherapy, in intermediate/high/very high risk cases, ENI is any longer needed?

3. Is ENI, associated or not to ADT, linked with an OS or bRFS survival advantage in patients submitted to adjuvant postsurgical prostate radiotherapy?
4. Additional toxicity due to the larger volumes treated might be reduced by more sophisticated radiotherapy techniques when ENI is added to prostate?
5. How many Radiation Oncology centers use ENI to treat patients with intermediate/high/very high-risk prostate cancer, with or without ADT?

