We propose a no-profit, multicenter observational study to collect data of consecutive patients treated with ENI both in the exclusive radical radiotherapy scenario and in the adjuvant postsurgical setting. Cases treated both with and without associated ADT will be recruited to evaluate Overall survival (OS) (that will be the main endpoint), Cause-specific (CSS) and Biochemical Relapse Free survival (bRFS), toxicity and Quality of Life (QoL) (the secondary endpoints).

Aims of the study

Clinical features and outcomes will be assessed as better detailed in the following lines:

1. To define the diffusion of the practice of treating pelvic lymph-nodes in patients affected by intermediate/high/very high risk non-metastatic prostate cancer (PCa) among Italian Radiation Oncology Centres, submitted to radical or post-operative radiotherapy;
2. To define the diffusion of the different radiotherapy techniques used to treat pelvic nodes and the other features of the radiation treatment;
3. To register prospectively biochemical and clinical failure, prostate cancer deaths and deaths for any cause in the population studied;
4. To register prospectively the toxicity due to radiotherapy and androgen deprivation therapy in patients treated with pelvic nodes radiotherapy;
5. To compare clinical outcomes and toxicities observed in the different clinical and therapeutic subgroups with the corresponding historical data relative to PCa patients treated with radiotherapy with or without elective pelvic nodal irradiation, already available in the existing AIRO (Italian Society of Radiation Oncology) databases;

6. To exploit the collected data to define the need and the features of a prospective randomized trial evaluating the efficacy of elective pelvic nodal irradiation in patients with intermediate/high/very high risk non-metastatic prostate cancer.
7. The data obtained from the present observational study will be helpful for designing a subsequent randomized controlled trial.

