In summary, the study aims at the definition of survival, toxicity and QoL data in a representative sample of intermediate, high and very high risk prostate cancer patients consecutively recruited in Italian Radiation Oncology Centres over two years. Parameters considered will be OS, CSS and bRFS, toxicity (rectal, bladder, bowel toxicity, according to CTCAE v.4 scale) and QoL (according to the SF-12 scale and UCLA-PCI scale). Primary end point will be OS. Secondary endpoints will be CSS, bRFS, gastrointestinal and genitourinary toxicity, QoL deterioration.

Study Design

This is a prospective, multicenter, observational cohort study aimed to describe the advantage/disadvantage of different treatments of patients with intermediate/high/very high risk prostate cancer, through a web-based database.

Study Duration

The recruitment period, taking into account the needed sample size (*v.infra*) will be of two years, followed by three-year follow up period for each patient, with an accrual of at least 400-500 patients.

Population, Procedures

The study will include all consecutive patients affected by intermediate, high or very high-risk prostate cancer that fit the inclusion criteria and who are evaluated at each Centre involved in the study. Patients may have already undergone or not to radical prostatectomy and/or pelvic lymphadenectomy.

Inclusion criteria

- Men older than or aged 18 years;
- Histologically confirmed intermediate, high or very high risk prostate cancer patients (NCCN classification: Intermediate Risk T2b and T2c or Gleason Score 7 or PSA value between 10 and 20 ng/mL; High risk: T3a or Gleason score 8-10 or PSA > 20 ng/ml; Very high risk: T3b-T4 or patients with multiple adverse risk factors reported in the high risk category that may be shifted in the very high risk group
- Patients eligible for -and actually submitted to- radical radiotherapy treatment (+/- androgen deprivation) or adjuvant radiotherapy treatment after surgery (radical prostatectomy +/- pelvic lymphadenectomy);
- No other synchronous or previous malignant tumor other than skin basal cell carcinoma;
- Patients able to understand and sign the appropriate informed consent;
- Patients able to fill the QoL questionnaire;

Exclusion criteria

- Patients aged less than 18;

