Centers involved will identify all the eligible cases with biopsy proven prostate adenocarcinoma. Patients who are candidate to get involved in the study will be contacted by the physician in charge of the study for each Center. **Every** prostate cancer patient consecutively evaluated at the recruiting Centers and planned to receive radical exclusive or post-operative radiotherapy will be registered; this registration includes demographic and staging results data; only intermediate, high, very high patients will have, however, treatment and follow up CRF compiled (both treated with or without ENI; +/- ADT).

Eligible patients will then receive all the information necessary to formulate their adhesion to the study and finally the physician will fill in the “Pretreatment” Case Report Form (CRF) that will include:

- Demographic Information (date of birth, study title, civil state, working information);
- Another person (relatives, friends,...) as a contact to minimize follow up loss;
- Anamnestic data (height, weight, smoking habit, comorbidities, Cumulative Illness Rating Scale [44], Attachment 1);
- Initial diagnosis (date; PSA at diagnosis);
- Risk factors;
- Staging (clinical TNM, date of biopsy, Gleason score, total number of samples, number of positive samples);
- Quality of life and symptoms caused by prostate cancer (using Italian UCLA Prostate Cancer Index) [45, 46];
- General quality of life (SF-12 Standard V1) [47].

The choice of the treatment will be done based on commonly used international guidelines and on the specific internal protocol of each participating Center.

Since this study is observational, involved patients will be treated following *good clinical practice* and institutional policies procedures.

Clinical outcomes, (such as overall survival and biochemical relapse free survival) and variables, demographic features, dosimetric analysis and acute/late toxicities of both RT and ADT will be reported.

Phase 3: Follow-up (1, 3, 6, 12, 18, 24, 30, 36 months)

After the end of the radiotherapy treatment patients will be evaluated 1, 3, 6, 12, 18, 24, 30 and 36 months since the last session.

Every patient will be contacted by the physicians to fill a CRF that will include:

- Vital state (mortality, date and causes of death) or loss to follow up;
- Last PSA value;

- Other treatments (drugs);

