- Treatment : type of treatment, start date, PSA value before treatment; if surgery type of surgery and pathological TNM, margins, Gleason Score, number of positive lymph nodes; if external RT (intent, modality, technique, dose/fraction, volumes, concomitant hormonal therapies); if brachytherapy (type, intent, dose); if hormone therapy (type of drugs, start and end date, total duration);
- Acute and late toxicities;
- Biochemical Relapse with PSA value and date of last PSA;
- Quality of life and symptoms due to prostate cancer (Italian UCLA-PCI);
- General quality of life SF-12.

Toxicity and response evaluation

The enrolled patients will undergo the first follow up visit one month after the end of radiotherapy. On that occasion, clinical examination will be performed and previously prescribed blood tests, if required, will be evaluated. Genitourinary and gastrointestinal toxicity due to radiation therapy for prostate cancer will be reported according to the NCI Common Terminology Criteria for Adverse Events (CTCAE) version 4 for adverse event (AE) reporting. The CTCAE version 4 is identified and located on the CTEP web site at:

http://ctep.cancer.gov/protocolDevelopment/electronic_applications/ctc.htm [48]

In addition, a Case Report Form (CRF) will be completed (see Attachment 2), regarding:

- Technical characteristics of the radiation treatment (dose, volume, technique, association or not with hormonal therapy);
- Quality of life and complications due to prostate cancer (according to Italian UCLA-PCI) [45, 46];
- General quality of life (SF-12 Standard V1) [47].

Thereafter patients will be evaluated at 3-months, 6-months and 12-months after the end of radiotherapy, and then every 6 months for at least 24 months. During all those scheduled follow up visits, PSA level (jointly with testosterone, in case of association with hormonal therapy) and

previously prescribed blood texts if required, will be evaluated. Patients will undergo clinical examination, and genitourinary and gastrointestinal toxicity will be assessed according to the CTCAE v4.0 classification scale). In addition, a CRF (see Attachment 3) will be completed at each visit, regarding:

- Survival status (mortality, date and cause of death) or exit from the study;
- If macroscopical recurrence or disease progression occurred, the radiological exams (if performed);
- Further treatments received/planned after radiotherapy;
- The last available PSA;

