- Quality of life and complications due to prostate cancer (Italian UCLA-PCI) [45, 46];
- General quality of life (SF-12 Standard V1) [47].

The Italian UCLA-PCI and SF-12 Standard V1 questionnaires reported in Attachment 2 and Attachment 3 [45, 46, 47] will be given by the referring physician and self-compiled by patients in physician's absence, eventually with the help of a nurse if necessary; thereafter, the referring physician will insert the data to the database.

Data Collection, Confidentiality

Data will be collected through an *ad hoc* web based software, built to guarantee:

1. Respect of the Italian laws and of the international rules about GMP and privacy, according also to the general principles fixed by the Helsinki declaration and its subsequent updates;
2. The anonymization of the patient records;
3. The possibility for each participating Center to have unrestricted access to its own data;
4. The restriction of the access to the full dataset composed by the sum of the records provided by the single Centers; this will be allowed only after the authorization of the PI and the Study Coordinator. Once the study will be completed, access to the whole database will be possible only after having obtained the authorization of the AIRO President in charge and of the AIRO Board;
5. The safe storage of the data, along with that of the previous AIRO-PCSG studies, along with.

The use of the software will be elucidated to the single participating Centers in *ad hoc* start up

meetings, to guarantee an appropriate and homogeneous data collection; a tool bar will however be devised, to automatically verify inconsistencies in the data collected.

Statistical Considerations

Sample size

From previous experiences of the AIRO PCSG [49, 50], at least 15-20 Radiotherapy Centers from different regions of the country will be able to participate to the study. It is conceivable an accrual of at least 400-500 patients within 2 years and a further follow up of at least 3 years for each patient. For intermediate and high risk patients, an overall survival at 5 years of 0.8 has been previously reported (RTOG 94-13) [51]. According to the primary end-point of the study, a sample size of 400 patients will allow to estimate a 5-year survival of 0.8 with 95% confidence interval of 0.76-0.84 [52].

Statistical Analyses

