
Acute Toxicities

Rectal Acute Toxicity (Grade)		Date Tox.	
Urinary Acute Toxicity (Grade)		Date Tox.	
Small Intestine Acute Toxicity (Grade)		Date Tox.	

GI Acute Toxicity (small bowel)

(see Table 1)

select (1=G0, 2=G1, 3=G2, 4=G3, 5=G4, 6=Unknown)

Date yyyy-mm-dd

Rectal Acute Toxicity

select (1=G0, 2=G1, 3=G2, 4=G3, 5=G4, 6=Unknown)

Date yyyy-mm-dd

Urinary Acute Toxicity

select (1=G0, 2=G1, 3=G2, 4=G3, 5=G4, 6=Unknown)

Date

Late Toxicity bladder/ rectum

select (1=Yes, 2=No, 3=Unknown)

Date yyyy-mm-dd

Proctitis

select (1=G0, 2=G1, 3=G2, 4=G3, 5=G4, 6=I Unknown)

Date yyyy-mm-dd

Cystitis

select (1=G0, 2=G1, 3=G2, 4=G3, 5=G4, 6= Unknown)

Date yyyy-mm-dd

Impotence

select (1=No, 2=Yes pre RT, 3=Yes post RT, 4= Unknown)

Date yyyy-mm-dd

Incontinence

select (1=No, 2=Yes pre RT, 3=Yes post RT, 4=Unknown)

TABLE 1 – Toxicity

RECTAL/SMALL BOWEL Acute TOX

G0: No Toxicity

G1: Increased alvus frequency not requiring any treatment. Rectal pain or abdominal pain not requiring any painkillers

G2: Diarrhoea, mucositis, rectal pain or abdominal pain requiring painkillers

G3: Diarrhoea requiring parenteral supportive care, severe mucositis or haematological alterations requiring treatment. Abdominal distension

G4: Acute or subacute obstruction, fistula or perforation, haemorrhage requiring blood transfusion. Abdominal pain or tenesmus requiring ileostomy

BLADDER Acute TOX

G0: No Toxicity

G1: Low urinary tract symptoms (LUTS) and dysuria not requiring any treatment

G2: LUTS, dysuria and urgency requiring treatment or anaesthetics

G3: Severe LUTS, urgency, dysuria, pelvic pain or bladder spasms and haematuria

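### The late bowel toxicity endpoint has no designated graded CRF field for the small bowel, and no acute/late cut-off is stated for any site

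*Combined protocol and SAP*

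**What the plan says.** The synopsis (End-points) lists as secondary "acute and late toxicity evaluation (rectal, bladder, bowel toxicity, according to CTCAE v.4 scale". The summary closing Aims of the study repeats the sites, "toxicity (rectal, bladder, bowel toxicity, according to CTCAE v.4 scale", without separating acute from late, and then words the secondary endpoint by system, as gastrointestinal and genitourinary. The synopsis row on visits and the Phase 2 and Phase 3 text also refer to both acute and late toxicity. Toxicity and response evaluation says that at the scheduled visits "genitourinary and gastrointestinal toxicity will be assessed according to the CTCAE v4.0 classification scale".

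Attachment 2 (1 month) and Attachment 3 (later visits, to 36 months) carry the same toxicity block. It grades acute toxicity for rectum, urinary tract and small bowel, with dates, and the small-bowel item refers the user to Table 1. The late part is headed "Late Toxicity bladder/ rectum" and holds graded proctitis and cystitis, plus ungraded impotence and incontinence. Table 1 has a combined rectal/small-bowel scale for acute effects only; its two late scales are proctitis and cystitis.

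**The concern.** The endpoint and the form that feeds it do not match. Rationale question 4 is whether "Additional toxicity due to the larger volumes treated might be reduced by more sophisticated radiotherapy techniques when ENI is added to prostate", and aim 4 is "To register prospectively the toxicity due to radiotherapy and androgen deprivation therapy in patients treated with pelvic nodes radiotherapy". The background links the advantage of IMRT in whole-pelvis treatment to bowel sparing, and Attachment 2 records small-bowel dose. The site without a late grade is therefore one that the protocol itself treats as relevant to ENI.

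If centres complete the forms exactly as written, the analyst has no designated late small-bowel grade to report. Because no cut-off is stated, the analyst also cannot tell on a common rule whether a rectal or bladder event belongs in the acute or the late block, since both blocks appear on every follow-up form.

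**Working it through.** The plan gives no figure for toxicity, so there is none to reproduce on this point. Its one design figure does not depend on toxicity: 0.8 ± 1.96 × √(0.8 × 0.2 / 400) = 0.8 ± 0.039, or 0.761 to 0.839, which matches the stated 0.76–0.84.

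**Step 1. Endpoint against form.**

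| Site | Synopsis endpoint | Acute grade, Attachments 2 and 3 | Late grade, Attachments 2 and 3 | Late scale, Table 1 |
|---|---|---|---|---|
| Rectum | acute and late | yes | yes, as proctitis | yes |
| Bladder | acute and late | yes, as urinary | yes, as cystitis | yes |
| Small bowel (inferred from bowel) | acute and late | yes | none | none |

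Graded acute sites: 3. Graded late sites: 2. Sites in the endpoint without a late grade: 3 − 2 = 1. The inference in the last row rests on two facts: bowel is listed apart from rectal, and small bowel is the third acute site on the CRF.

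**Step 2. Is there an implied cut-off?** No. Late items are already on the 1-month form, and acute items are still on the form used to 36 months. Neither the text nor the layout separates the two periods.

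**Step 3. Where can a late small-bowel event go?**

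- *Acute small-bowel item.* It is dated, so the event can be reclassified once a cut-off exists, but its grade uses the acute definitions.
- *Proctitis.* The event is attributed to the rectum and enters the late rectal grade.
- *Gastro-intestinal entry under new comorbidities (Attachment 3).* This is free text with no grade.
- *Nowhere.*

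No section directs the centre to any of these.

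**Step 4. Do the routes give the same grade?** Not always. In Table 1, diarrhoea reaches G3 on the acute scale (parenteral support) but stops at G2 under proctitis. Abdominal pain and distension have acute grades but no proctitis entry. Fistula and perforation are G4 on both. Obstruction and haemorrhage carry different qualifiers on the two scales, so agreement depends on the case. These differences matter only for events that are filed by different routes.

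**Step 5. Grading system.** The narrative names CTCAE v4, while the small-bowel item points to the study's own Table 1. Neither text says how the two relate.

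**Step 6. Visit list.** Phase 3 says "patients will be evaluated 1, 3, 6, 12, 18, 24, 30 and 36 months since the last session". The heading of Attachment 3 includes 9 months and omits 30. Either list gives 7 time points after month 1, so the form gap is the same, but the lists conflict and must be reconciled.

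**The case against.** The strongest reply is that the endpoint is also worded as gastrointestinal and genitourinary toxicity. On that wording each system has a late graded item, and the proctitis scale includes diarrhoea, obstruction, perforation and fistula. This stands as a real ambiguity. It does not remove the problem: both places that name sites list bowel apart from rectal, and a proctitis grade cannot show which part of the bowel was affected.

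Second, the acute small-bowel item is dated and present to 36 months, so late events filed there can be recovered. This also stands, in part. It needs a cut-off that the plan does not give, and the grade remains an acute-scale grade.

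Third, the start-up meetings are intended "to guarantee an appropriate and homogeneous data collection; a tool bar will however be devised, to automatically verify inconsistencies in the data collected". These measures may make centres more consistent, but they do not create a field or a cut-off.

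Fourth, the operative instrument is a web portal that is not in the documents, and the CRF text available may be incomplete. This is a fair caveat. However, the toxicity block and Table 1 are legible and agree across both attachments.

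A reader might infer that late bowel toxicity goes uncollected, or that the ENI comparison is biased. The documents support neither. Gastrointestinal toxicity is assessed at each scheduled visit, the UCLA-PCI bowel items are collected (as patient-reported quality of life, not toxicity grades), and nothing gives the frequency of misfiled events or their relation to ENI. Nor should the gap be counted once per visit: it is one block repeated on two forms. The opposite inference, that late rectal and bladder grades are clean, also fails, because of proctitis misfiling and the missing cut-off.

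**Conclusion.** The point holds and should be fixed. In the CRF text available, one of the three sites named in the late-toxicity endpoint has no designated late grade, and the acute/late boundary is undefined for all three.

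Part of the loss is recoverable by date. What remains is events filed elsewhere or never recorded, plus grades taken from an unsuitable scale. The number of events and the direction of any bias cannot be derived from the documents. Overall survival and the sample size are unaffected. The plan specifies no dose–toxicity model, so none is claimed to be damaged.

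The conclusion rests on two assumptions: that bowel in the endpoint means small bowel, and that the portal follows the attachments.

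**What to change.** 1. Add one dated late small-bowel toxicity grade to Attachment 3, separate from proctitis and graded by the CTCAE v4 system that the endpoint names.
2. State one acute/late cut-off for all sites, counted from the end-of-treatment date recorded in Attachment 2.
3. Reconcile Table 1 with CTCAE v4, and the Attachment 3 visit list with Phase 3.
4. For data already entered, classify dated acute-item entries by that cut-off and flag that they were graded on the acute scale. Query gastro-intestinal comorbidity text and late proctitis entries that could be small-bowel. State that events never recorded cannot be recovered.

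The cost is a small CRF and database amendment, a site instruction, some data queries, and any ethics step the amendment requires, since each centre has its own committee approval. The date classification can be programmed over at most 400 × 7 = 2,800 to 500 × 7 = 3,500 Attachment 3 forms, assuming every form is completed. The number of queries is unknown. No new visit, test or staff is needed, because gastrointestinal toxicity is already assessed at the scheduled visits.
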